1.1 Longitudinal Trial

The trial profile is given in the Manual of Operations. In the longitudinal trial, children are randomized to two arms: **Azithro** and **Control**. The trial is a placebo-controlled, double-masked (i.e., double-blind), individual-randomized clinical trial.

Objectives.

Determine the effect of a single dose of azithromycin for children aged 8 days-59 months on longitudinal changes in the intestinal microbiome over a 6-month period. Children under 5 years of age will be randomized to a single dose of azithromycin or placebo. We hypothesize that children randomized to a single dose of azithromycin will exhibit a significant difference in the intestinal microbiome after a 6-month period, compared to those randomized to placebo.

Determine the effect of a single dose of azithromycin for children aged 8 days-59 months on child growth over a 6-month period. We hypothesize that a single dose of azithromycin will significantly increase child growth over a 6-month period, compared to single dose of placebo.

2 Statistical Analysis

2.1 Planned Analyses

2.1.1 Longitudinal Trial

Four hundred fifty children between the ages of 8 days and 59 months may be enrolled in the trial and be offered placebo or azithromycin in a masked fashion. Relevant indicators will be collected using whole blood venipucture, nasopharyngeal swabs, fresh frozen stool, rectal swabs, and anthropometry measurements at days 0, 14, and 180. Children followed up within day 120 and day 240 will be included in primary day 180 analysis. Fifty randomly selected children (25 per arm) will have an additional rectal swab collected at days 2, 4, 6, 8, 10, 12 post-treatment.

Primary Analyses. Pairwise comparison of *Campylobacter*, *C. upsaliensis* and *C. hominis* using Fisher's exact test, corrected for multiple comparisons using Holm-Bonferroni method.

We will compare profile of *Campylobacter*, *C. upsaliensis* and *C. hominis* based on L_1 , L_2 distance, and PERMANOVA. We will compare diversity between arms at days 14 and 180 separately, using Shannon's Index and Simpson's Index.

Statistical considerations.

- Model adequacy will be checked by examination of residuals or other goodness of fit tests as needed. Inadequate model fit will prompt us to report alternative models.
- Multiple imputation will be used in case of missing baseline covariates (if applicable). Missing outcome variables will be handled by sensitivity analysis and reporting of conditional results.
- False Discovery Rate will be calculated for each estimated significant effect.

Secondary analyses.

Note that participants outside of WHO Child Growth Standards for WAZ (-6 to +5 SD), HAZ (-6 to +6 SD), or WHZ (-5 to +5 SD) will be excluded from all anthropometric analyses.

S. pneumoniae carriage and macrolide resistance Separate Fisher's exact test at days 14 and 180.

lytA occurence Separate Fisher's exact test at days 14 and 180.

erm B, mef A, pp2A Separate Fisher's exact test at days 14 and 180.

N. meningitides, H. influenzae, Moraxella, S. aureus Pairwise comparison of organisms using Fisher's exact test, corrected for multiple comparisons using Holm-Bonferroni method.

PERMANOVA of L_1 and L_2 distance of bacterial reads. Shannon's and Simpson's estimated gamma diversities will be compared by arm.

Malaria Fisher's exact test of parasitemia and clinical malaria at days 14 and 180.

- weight gain Defined as grams per kilogram per day (g/kg/day) will be compared between arms separately at days 14 and 180 using linear regression. Baseline weight is accounted for in our metric of weight gain and will not be included in the regression analysis. We will use ordinary least squares method of estimatation and permutation tests to estimate coefficient p-values.
- HAZ, WAZ, WHZ, MUAC As secondary analysis, we will perform separate ANCOVA of anthropometric indicators at days 14 and 180, adjusting for baseline.

3 Sample Size Considerations

We assume a mean (standard deviation) alpha Shannon's index of 16.47 (7.12) using results from Thuy et al. [DAR⁺17]. Assuming 80% power and detectable effect size of 1.02 standard deviations and no loss to follow-up, we propose a sample size of 225 per group, totaling 450 study participants.

4 Randomization

The randomization will be conducted using R. The function sample with option replace=FALSE will be used to conduct the random shuffling. Note that the choice of the random number seed completely determines the randomization. To ensure the integrity of the randomization, we will use the procedure we used for MORDOR/Malawi.

Samples will be randomly grouped into 5-pools for processing, within an arm and a time point.

5 Abbreviations

ANCOVA Analysis of covariance

- $\mathbf{DSMC}\,$ Data and Safety Monitoring Committee
- ${\bf HAZ}$ height for age Z score
- MUAC Mid upper arm circumference
- ${\bf SAP}\,$ Statistical Analysis Plan
- \mathbf{WAZ} weight for age Z score
- \mathbf{WHZ} weight for height Z score

References

[DAR⁺17] T. Doan, A. M. Arzika, K. J. Ray, S. Y. Cotter, J. Kim, R. Maliki, and et al. Gut microbial diversity in antibiotic-naive children after systemic antibiotic exposure: A randomized controlled trial. *Clinical Infectious Disease*, 64, 2017.

6 Revision History

- 29 May 2019 Revised specification and wording of primary and secondary outcomes. Moved weight gain to secondary outcome. Clarified Bonferroni correction for certain species.
- 13 Jan 2020 Updated the pre-specified sample size for the sub-section of GAMIN sample (GAMIN QOD).
- 16 Jan 2020 Abbreviated the study name on title page.
- 20 Mar 2020 Added sample size considerations section and specification of day 180 time window.
- 08 May 2020 Specified WHO standard range for inclusion for anthropometric (child growth) analysis.
- 02 Jul 2020 Increased upper range of day 180 window from day 210 to day 240.
- 20 Oct 2021 Specified 5-pool test in sample randomization. Removed duplicated S. pneumoniae.

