3.2 Sample Size

We will enroll up to 1500 children into the two study arms (725/arm). In the sub-study, 25 children per arm will be randomized. This sample size is based on the primary outcome, Simpson's alpha diversity in the intestinal microbiome. We will base some statistical assumptions on preliminary data from the Nouna HDSS. For instance, we assume a 15% loss to follow-up, a baseline effective number of 9, and a standard deviation of 0.7.

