	Fresh Frozen Stool	
	\Box IHPS follow-up on	
	neonates	
	□ Vital Status	
	□ Adverse Events	
	survey	
Day 21	IHPS follow-up on	□ Form 7: IHPS
Day 180 (nuiman) autooma)	neonates	
Day 180 (primary outcome) *Includes window of 120-210 days	AnthropometryWhole Blood	Form 3: Follow-up
includes window 0j 120-210 ddys	\square Blood Smear	Registration Form 4: Exams
		\Box Form 4: Exams \Box Form 7: Vital
	TemperatureNP swab	Status, AE, IHPS
	\square Rectal Swab	Status, AE, IIII S
	\Box Fresh Frozen Stool	
	□ Vital Status	

Day 730 (2 Year Follow-Up)		
	□Rectal Swab	□Form 4: Exams

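### The protocol points to Simpson's alpha diversity at day 180 as primary, but the SAP lists that test unranked among several primary analyses with no working overall error control, and assigns no clear analysis to the Objective 3 primary outcome

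*SAP*

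**What the plan says.** **Protocol, Objective 1.** Section 3.2 states: "This sample size is based on the primary outcome, Simpson's alpha diversity in the intestinal microbiome". In Table 1 (Chapter 4) the six-month visit is labelled "Day 180 (primary outcome". No single sentence joins index and day. Section 3.5 is broader: it speaks of microbiome change over six months, measured at every follow-up, and names no index. Its Campylobacter and PERMANOVA items are secondary outcomes, confined to the 50-child rectal swab cohort in the first two weeks.

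**SAP, Objective 1.** The hypothesis in section 1.1 is that treated children will "exhibit a significant difference in the intestinal microbiome after a 6-month period". The Primary Analyses in section 2.1.1 list:
- "Pairwise comparison of *Campylobacter*, *C. upsaliensis* and *C. hominis* using Fisher's exact test, corrected for multiple comparisons using Holm-Bonferroni method";
- a comparison of the profile of the same organisms by L1 distance, L2 distance and PERMANOVA;
- "We will compare diversity between arms at days 14 and 180 separately, using Shannon's Index and Simpson's Index".

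No day is given for the first two items, and nothing is ranked. The visit-window rule just above does refer to day 180 as the primary analysis. Section 3 sizes the trial on a different index: "We assume a mean (standard deviation) alpha Shannon's index of 16.47 (7.12".

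**SAP, error control.** Holm is attached to the Campylobacter Fisher set and to one secondary set of organisms. The general statement is "False Discovery Rate will be calculated for each estimated significant effect". The only numerical alpha, 0.001, is in the Introduction and applies to unplanned analyses.

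**Objective 3.** Protocol 3.5 places macrolide resistance determinants under its Primary Outcome heading, measured by sequencing in the 50-child cohort and again from a rectal swab at two years. SAP 1.1 lists only Objectives 1 and 2. The SAP's nearest item is a secondary line for ermB, mefA and a third target: "Separate Fisher's exact test at days 14 and 180". It names no swab type. The SAP does not mention the two-year swab.

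**The concern.** Both documents state a hypothesis of a significant difference, so a reader needs to know which result will decide it. The protocol allows a reasonable inference. The SAP, which governs the analysis, places that test beside others of equal standing and attaches a multiplicity correction to only one group. With no ranking and no rule for combining results, the headline finding could be chosen once the results are known, and the error rate of the microbiome claim is undefined. For Objective 3, a reader could not tell which analysis answers an outcome that the protocol calls primary.

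**Working it through.** **1. The plan's own sample size.** This shows whether a multiplicity allowance was built in. Inputs from SAP section 3: effect 1.02 SD, 80% power, no loss, 225 per group. Alpha is not stated; two-sided 5% is assumed.

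n per group = 2(1.960 + 0.842)² / 1.02² = 15.1, so 16.

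Reading 1.02 as a raw difference with SD 7.12 gives 2(1.960 + 0.842)²(7.12/1.02)² = 764.9, so 765. Alpha of 0.05/4, 0.05/7 and 0.001 give 22, 24 and 33. None gives 225, so the stated size is no evidence of an adjustment. The failure to reproduce 225 is a separate matter, and nothing below depends on it.

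**2. Counting the primary block.** The Holm set counts as one unit, because Holm holds it at 5% overall.

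| Reading | Units |
|---|---|
| Simpson, day 180 | 1 |
| Shannon and Simpson, day 180 | 2 |
| Both indices, both days | 4 |
| Plus one Holm set and two PERMANOVA tests (L1, L2) | 4 + 1 + 2 = 7 |
| Holm set and PERMANOVA at both days as well | 4 + 2 + 4 = 10 |

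The SAP gives no day for the Fisher and PERMANOVA items, so either of the last two rows is possible. Whether L1, L2 and PERMANOVA make one test or two is also unclear; two is assumed.

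**3. Chance of at least one false positive.** Assumptions not in the documents: 5% per unit, no true effect, and any one significant result supports the claim. With independent units the chance is 1 − 0.95^k.

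| k | Result |
|---|---|
| 1 | 5.0% |
| 2 | 9.8% |
| 4 | 18.5% |
| 7 | 30.2% |
| 10 | 40.1% |

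**4. Allowing for correlation** (values assumed).
- Two indices at day 180, bivariate normal: 7.8%, 7.0% and 6.5% at correlations 0.8, 0.9 and 0.95.
- Four diversity tests, simulated: 13.2% at 0.9 between indices and 0.3 between days; 11.6% to 15.1% over index correlations 0.8 to 0.95 and day correlations 0 to 0.5.
- Seven units, with the other three independent: 1 − (1 − 0.132) × 0.95³ = 25.6%. With correlation across families and a conservative Fisher set as well, simulation gave 17% to 26%.
- Ten units, with the other six independent: 1 − (1 − 0.132) × 0.95⁶ = 36.2%.

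**5. Objective 3, side by side.**

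| | Protocol 3.5 | SAP 2.1.1 |
|---|---|---|
| Status | Primary | Secondary |
| Sample | Rectal swab | Not stated |
| Children | 50-child cohort | Not stated |
| Days | 0 to 14 every second day, and 180 | 14 and 180 |
| Method | DNA sequencing | Named genes, Fisher's exact test |
| Two-year swab | Listed | Absent |

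**The case against.** **The SAP does single out day 180.** Its visit-window rule calls day 180 the primary analysis, in agreement with the protocol's Table 1 and the SAP hypothesis. This counts against treating day 14 as an equal route. But the rule says who is included; it does not choose an index or demote the day 14 comparisons in the same block.

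**The documents overlap.** A reader might infer that the two documents yield different primary results. That goes too far: Simpson at day 180 is in the SAP's primary block. What is missing is its rank.

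**An inflated error rate is not established.** A reader might conclude that the plan's error exceeds 5%. The SAP never says that any one significant result suffices. If its block is read through the protocol's labels, one test remains and the error is 5%. The excess is conditional. Nor is 30% a ceiling, since the undated items may be run twice.

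**Error control is planned.** If the false discovery rate sentence meant Benjamini-Hochberg at 5% over the seven units, the false-claim chance with no true effect would be 4.1% to 4.6%. The sentence says none of this, and as worded it applies only to effects already called significant.

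**The resistance tests may cover rectal samples.** Protocol 6.1 ties ermB and mefA to pneumococcal isolates, which tempts one to read the SAP line as nasopharyngeal only. Protocol 4.11, however, lists targeted PCR for erm, mef and mph on rectal and nasopharyngeal swabs at days 0, 14 and 180. So that reading is not secure. The mismatch with a sequencing outcome in 50 children remains.

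**Simpson at day 180 is itself assembled** from two places in the protocol. That is true, and it is a further reason to state it in one sentence.

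**Conclusion.** The point stands as a defect of specification. For Objective 1 the SAP does not say which analysis in its primary block decides the claim, it sizes on Shannon where the protocol sizes on Simpson, and its overall error control cannot be applied as written. Under the two assumptions of 5% per test and any one result sufficing, the false-claim chance runs from 9.8% (two indices at day 180) through 18.5% and 30% to 40% (ten units) if independent; for the two-index case it is 6.5% to 7.8% at correlations of 0.95 to 0.8. With one named test it is 5%. The gap in ranking needs none of these assumptions.

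For Objective 3, no SAP analysis is clearly assigned to the protocol's primary outcome, and none covers the two-year swab. It cannot be said that resistance goes unanalysed, only that the match is not stated. This should be put right before the results are reported.

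**What to change.** 1. In SAP 2.1.1, name one primary test for Objective 1: Simpson's alpha diversity in intestinal samples at day 180, azithromycin against placebo, two-sided 5%. State the unit of analysis: the child, or the five-sample pool of SAP section 4.
2. Label Shannon, day 14, PERMANOVA and Campylobacter as secondary, and use the same index in SAP section 3.
3. For Objective 3, either name one rectal-swab resistance test at one time point as the primary analysis of the 50-child cohort, or relabel the outcome secondary in protocol 3.5. State where the two-year swab is analysed.
4. Give the false discovery rate sentence a level and a family, for example Benjamini-Hochberg at 5% over the secondary microbiome and resistance tests.
5. Date the change in the SAP revision history and state whether arm-level data had been seen. Protocol 4.6 puts baseline visits in November 2019, so this is a late change.

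**Cost.** Some analyses lose the primary label and none is dropped. The day 180 test loses no power if it keeps its full 5%. Only if the team chose to share 5% between Objectives 1 and 3 by Holm would there be a price: at worst, the difference detectable with 80% power at 225 per arm would rise from 0.265 to 0.291 SD.

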3.5 Outcomes

Primary Outcome

- Changes in intestinal microbiome over a 6-month period (Objective 1). Microbiome diversity will be measured at all follow-up time points.
 - Whole Blood Venipuncture. Whole blood venipuncture will be collected at all follow-ups. We will measure cell-free DNA and inflammatory markers such as C-reactive protein.
 - **Nasopharyngeal Swabs.** NP swabs will be collected at all follow-up time points. We will collect data on phenotypic resistance of *S. pneumoniae*, evaluate the microbiome using next-generation sequencing, and monitor genotypic resistance among various organisms.
 - **Fresh Frozen Stool**. FFS will be collected at all follow-ups. We will be looking for IgA-bound bacteria from the small intestine and evaluating inflammatory markers such as C-reactive protein.

- **Rectal Swabs**. We will collect rectal swabs at all time points. We will monitor genotypic resistance of various organisms with targeted PCR and evaluate the microbiome using next-generation sequencing.
- **Presence of macrolide genetic resistant determinants (Objective 3).** Macrolide resistance will be measured from a sample of participants.
 - Rectal Swab Cohort. We will collect rectal swabs from 50 children at days 0, 2, 4, 6, 8, 10, 12, 14 and 180 post-treatment. Macrolide resistance will be analyzed using DNA sequencing.
 - **2 Year Timepoint.** We will collect rectal swabs from all kids 2 years postenrollment to evaluate macrolide genetic resistance determinants.

Secondary Outcomes

- Child growth over a 6-month period (Objective 2). Anthropometry measurements will be collected at all follow-up time points. Weight gain will be defined as grams per kilogram per month (g/kg/month).
 - MUAC. Mid-upper arm circumference will be measured at all follow-ups
 - **WAZ.** Weight will be measured at all follow-ups and weight-for-age z-scores will be calculated
 - WHZ. Weight and height will be used to calculate weight for height z-scores
 - **HAZ.** Height or length will be measured at all follow-ups and height-for-age z-scores will be calculated.
- Mortality by 6-months. Vital status will be assessed at all follow-up visits. Mortality will be defined as death within the study period. Date of death will be collected.
- Adverse events. Adverse events will be reported at all follow-ups.

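### One out-of-range z-score, at an unstated visit, removes the whole child from every growth analysis, including outcomes that use neither length nor age

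*SAP*

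**What the plan says.** The rule opens the secondary analyses in SAP section 2.1.1. It names "participants outside of WHO Child Growth Standards for WAZ (-6 to +5 SD), HAZ (-6 to +6 SD), or WHZ" and continues "or WHZ (-5 to +5 SD) will be excluded from all anthropometric analyses". It does not say at which visit a z-score must be out of range.

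Two sets of growth analyses follow in the same section:

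- **HAZ, WAZ, WHZ and MUAC.** These share one entry: "we will perform separate ANCOVA of anthropometric indicators at days 14 and 180, adjusting for baseline". MUAC is thus expressly an anthropometric indicator.
- **Weight gain.** It has its own entry: "Defined as grams per kilogram per day (g/kg/day) will be compared between arms separately at days 14 and 180". The exclusion sentence does not name it.

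Two other places bear on whether weight gain is covered. Protocol section 3.5 places it under the child growth outcome: "Anthropometry measurements will be collected at all follow-up time points. Weight gain will be defined as grams per kilogram per month". The SAP revision history entry of 08 May 2020, which introduced the rule, reads "Specified WHO standard range for inclusion for anthropometric (child growth) analysis". (The two documents express weight gain per month and per day respectively. That does not affect this point.)

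On timing, the SAP schedules "anthropometry measurements at days 0, 14, and 180", and protocol section 3.3 puts the baseline measurements before randomization.

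**The concern.** The WHO limits screen out z-scores that are probably measurement or recording errors. Such an error belongs to a particular measurement, and so to particular indices at a particular visit. The SAP rule removes the child instead. A faulty length makes HAZ and WHZ unusable but says nothing about MUAC or weight gain, and those are removed too.

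The silence on visits adds a second problem. Days 14 and 180 come after treatment, and the z-scores at those visits are themselves outcomes. If they can trigger the rule, membership of the analysis set may depend on the outcome. On the widest reading, a day 180 value would take a child out of the day 14 comparison. Two analysts could build different analysis sets from the same sentence.

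At stake is the growth objective, which is the second objective in both documents. The primary microbiome analysis is not touched.

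**Working it through.** **Step 1. What each kind of error spoils.** This follows from the definitions of the indices.

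| Error in | WAZ | HAZ | WHZ | MUAC | Weight gain |
|---|---|---|---|---|---|
| Length or height | no | yes | yes | no | no |
| Age | yes | yes | no | no | no |
| Weight | yes | no | yes | no | yes |

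For length and age errors, removing MUAC and weight gain loses sound data. For a weight error, removing weight gain is reasonable. MUAC is unaffected in all three rows.

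**Step 2. How many children.** The documents give no expected number of exclusions, so there is no figure to reproduce. Let p be the chance that a child is flagged at a visit, with the indices flagged together because they share length, weight or age. I assume p = 0.25% to 1%, independent between visits. The loss over k visits is 1 − (1 − p)^k. Counts use the SAP's 450 children.

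| Visits that can trigger the rule | k | p = 0.25% | p = 1% |
|---|---|---|---|
| Baseline only | 1 | 0.25% (about 1) | 1.0% (about 4 or 5) |
| Days 14 and 180 only | 2 | 0.5% (about 2) | 2.0% (about 9) |
| Any of the three | 3 | 0.75% (about 3) | 3.0% (about 13) |

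For example, 1 − 0.99³ = 0.0297, and 0.0297 × 450 = 13.4. With the protocol's 725 per arm (1,450 children), the last row is about 11 to 43 children. An age error carried from the baseline questionnaire would tend to recur at each visit, which would make the three-visit total smaller.

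**Step 3. The comparator.** With deletion by index and visit, a length or age error removes no child from MUAC or weight gain. Each z-score ANCOVA needs a valid baseline and a valid follow-up value, so it loses 1 − (1 − p)² = 0.5% to 2.0%. If the baseline value is imputed, as the SAP allows for missing baseline covariates, it loses only p = 0.25% to 1%.

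**Step 4. Precision.** The detectable difference in SD units is (1.960 + 0.842) × √(2/n), for 80% power and an assumed two-sided 5% level.

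- n = 225 per arm: 0.264 SD.
- After a 0.75% loss, n = 223.3: 0.265 SD.
- After a 3.0% loss, n = 218.3: 0.268 SD.

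**Step 5. Selection, if follow-up values count.** Suppose treatment truly raises WHZ by 0.2, WHZ is normal with mean μ and SD σ, and values below −5 are cut. The mean of those kept is μ + σφ(a)/(1 − Φ(a)), with a = (−5 − μ)/σ. All inputs are assumed.

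| Control mean, SD | Estimated effect after the cut |
|---|---|
| −1.0, 1.1 | 0.200 |
| −1.5, 1.5 | 0.189 |
| −1.5, 1.8 | 0.177 |

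In the widest case, 2.6% of control and 2.0% of treated children are cut. The distortion is slight unless the spread is wide.

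**The case against.** **The trigger visit is unstated.** A reader might infer that the rule necessarily conditions on post-randomization outcomes. The text does not establish this. The SAP analyses days 14 and 180 separately, so a visit-by-visit reading is possible. So is a baseline-only reading, and baseline precedes randomization. This part of the objection stands: outcome dependence is possible, not shown.

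**Weight gain is not named, and has an entry separate from the anthropometric indicators.** This is true. Even so, the revision history equates anthropometric with child growth, and protocol section 3.5 defines weight gain within child growth, so coverage is the natural reading. MUAC is covered on the SAP's own words.

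**Not everything discarded is valid.** This stands. A wrong weight corrupts WAZ, WHZ and weight gain together, and the planned least-squares analysis of weight gain is sensitive to outliers. Keeping weight gain unconditionally would be wrong.

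**A larger loss might be inferred** by treating the three indices at three visits as nine independent chances: 1 − (1 − p)^9 gives 2.2% to 8.6% for p = 0.25% to 1% per z-score. That contradicts the mechanism, because one faulty length or age flags two indices together. The nine-flag figure is an upper bound at those rates.

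**Flags may be rare.** Protocol sections 9.2 to 9.4 have length, height and weight each taken three times, so one stray reading need not produce an implausible z-score. This helps, although the documents do not say how the three readings are combined.

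**The SAP already plans sensitivity analysis for missing outcomes.** That provision is general and not tied to this rule. The SAP introduction defines sensitivity analyses in terms of the primary outcome, and growth is secondary.

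**Conclusion.** The concern holds as an over-broad and under-specified exclusion rule. As written, an implausible length or age at an unstated visit removes the child's MUAC and, on the natural reading, weight gain, although neither depends on length or age. Whether the rule also selects on post-randomization outcomes depends on a visit definition that the SAP does not give.

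The size is modest. About 0.75% to 3.0% of children are lost from every growth analysis if all three visits count. This rests on an assumed flag rate of 0.25% to 1% per visit, indices flagged together, and independence between visits. The detectable difference moves from 0.264 SD to at most 0.268 SD under those assumptions. Only secondary analyses are affected.

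A reader might also infer from the date of the rule that it was prompted by the data. It was added on 08 May 2020, and protocol section 4.6 dates the baseline malaria tests for 450 children to November 2019 and day 14 testing to December 2019. Nothing in the documents supports that inference: the limits are described as WHO limits and the trial is masked. The late date is only a further reason for explicit wording.

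**What to change.** Replace the exclusion sentence in SAP section 2.1.1 with wording such as:

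> A z-score outside the WHO limits is set to missing for that index and that visit only. MUAC is kept. Weight gain is kept unless the weight at baseline or at that visit is itself judged implausible (for example, WAZ and WHZ both flagged, or a separate pre-specified limit on weight change).

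Then add two items:

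- Report the number of flagged values by arm and visit.
- Run one sensitivity analysis of the growth outcomes with no z-score exclusions. This is needed because deletion by index still removes a genuinely extreme follow-up WHZ from the main WHZ analysis. The rewording alone does not remove that selection.

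If the sponsor meant baseline z-scores only, the SAP should say so. The limitation by index would still be worth making.

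The cost is a short change to the SAP and the matching code, with no new data. The downside is a little more analysis work and slightly different numbers of children across the growth analyses, which the tables should show.
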